11.7 Interim analyses

Corporate Confidential Information

12 Ethical considerations

12.1 Regulatory and ethical compliance

This clinical study was designed and shall be implemented and reported in accordance with the ICH Harmonized Tripartite Guidelines for Good Clinical Practice, with applicable local regulations (including European Directive 2001/20/EC, US Code of Federal Regulations Title 21, and Japanese Ministry of Health, Labor, and Welfare), and with the ethical principles laid down in the Declaration of Helsinki.

12.2 Responsibilities of the investigator and IRB/IEC

Before initiating a trial, the investigator/institution should obtain approval/favorable opinion from the Institutional Review Board/Independent Ethics Committee (IRB/IEC) for the trial protocol, written informed consent form, consent form updates, subject recruitment procedures (e.g. advertisements) and any other written information to be provided to subjects. Prior to study start, the investigator is required to sign a protocol signature page confirming his/her agreement to conduct the study in accordance with these documents and all of the instructions and procedures found in this protocol and to give access to all relevant data and records to Novartis monitors, auditors, Novartis Quality Assurance representatives, designated agents of Novartis, IRBs/IECs, and regulatory authorities as required. If an inspection of the clinical site is requested by a regulatory authority, the investigator must inform Novartis immediately that this request has been made.

For multi-center trials, a Coordinating Investigator will be selected by Novartis around the time of Last Patient Last Visit to be a reviewer and signatory for the clinical study report.

12.3 Publication of study protocol and results

Novartis assures that the key design elements of this protocol will be posted in a publicly accessible database such as clinicaltrials.gov. In addition, upon study completion and finalization of the study report the results of this trial will be either submitted for publication and/or posted in a publicly accessible database of clinical trial results.

13 Protocol adherence

This protocol defines the study objectives, the study procedures and the data to be collected on study participants. Additional assessments required to ensure safety of subjects should be administered as deemed necessary on a case by case basis. Under no circumstances should an investigator collect additional data or conduct any additional procedures for any research related purpose involving any investigational drugs.

Investigators must apply due diligence to avoid protocol deviations. If the investigator feels a protocol deviation would improve the conduct of the study this must be considered a protocol amendment, and unless such an amendment is agreed upon by Novartis and approved by the IRB/IEC/REB it cannot be implemented. All significant protocol deviations will be recorded and reported in the CSR.

Sample labeling and shipping instructions will be provided in a separate laboratory manual.

20 Appendix 6: ESSDAI

Will be provided as a separate document.

21 Appendix 7: ESSPRI

Will be provided as a separate document.

22 Appendix 8: SF-36

Will be provided as a separate document.

23 Appendix 9: MFI

Will be provided as a separate document.

1.1 Scope of document

The RAP documents contain detailed information to aid the production of Statistics & Programming input into the Clinical Study Report (CSR) for trial “*CCDZ173X2203*”.

The Statistical analysis plan (SAP) describes the implementation of the statistical analysis planned in the protocol.

1.2 Study reference documentation

This SAP has been developed using Clinical Trial Protocol version v00 (original protocol) dated 26 January 2016.

1.3 Study objectives

1.3.1 Primary objectives

- To assess the safety and tolerability of CDZ173 in patients with primary Sjögren’s syndrome (pSS).
- To compare the effect of CDZ173 versus placebo on the patient reported outcome (ESSPRI) of pSS patients after 12 weeks of treatment (study week 13).

1.3.2 Secondary objectives

- To assess the pharmacokinetics of CDZ173 in pSS patients.
- To evaluate the effect of CDZ173 versus placebo on clinical disease outcomes (ESSDAI, SF-36, MFI) in pSS patients after 12 weeks of treatment (study week 13).
- To evaluate the changes in the physician global assessment of the patient's overall disease activity after 12 weeks of treatment (study week 13).
- To evaluate the changes in the patients’ self-reported global assessment of their disease activity after 12 weeks treatment (study week 13).

1.3.3 Exploratory objectives

Corporate Confidential Information

Corporate Confidential Information

1.4 Study design and treatment

This is a double-blind, randomized, placebo-controlled, parallel design, non-confirmatory study to assess the safety, tolerability, pharmacokinetics and preliminary clinical efficacy of multiple oral doses of CDZ173 (70 mg b.i.d.) in patients with pSS.

The study will consist of a 4-week screening period, a baseline period prior to randomization, a 12-week treatment period and a 4-week follow-up period (no study drug or study visits) before the End of Study visit. The total duration for each patient in the study will be approximately 21 weeks.

Approximately 27 patients will be randomized (2:1) to a 12 week treatment receiving either CDZ173 or placebo. Randomization will be stratified according to baseline glucocorticoid intake (yes/no).

For the entire duration of the treatment period (12 weeks), patients will receive a b.i.d. dosing regimen to be administered at approximately 12 h intervals.

[figure not shown]
Safety assessments will include physical examinations, ECGs, vital signs, standard clinical laboratory evaluations (hematology, biochemistry and urinalysis) as well as adverse event and serious adverse event monitoring.

Corporate Confidential Information

Other assessments to be completed are outlined in the Assessment schedule in the protocol.

The study design is summarized in Figure 1-1 below:

Figure 1-1 Study Design

2 First interpretable results (FIR)

Corporate Confidential Information

Corporate Confidential Information

3 Interim analyses

Corporate Confidential Information

4 Statistical methods: Analysis sets

For subjects for whom the actual treatment received does not match the randomized treatment, the treatment actually received will be used for the analysis.

All subjects that received study drug and with no protocol deviations with relevant impact on safety will be included in the safety analysis set.

The PK analysis set will include all subjects with at least one available valid (i.e. not flagged for exclusion) PK concentration measurement, who received any study drug and experienced no protocol deviations with relevant impact on PK data.

The PD analysis set will include all subjects with any available baseline and post-dose PD data, who received any study drug and experienced no protocol deviations with relevant impact on PD data.

The analysis sets and protocol deviation codes are related as follows:

Table 4-1 Protocol deviation codes and analysis sets

Category Deviation code	Text description of deviation	Data exclusion
Subjects are excluded from all (safety) analysis in case of these Protocol deviations:		Exclude subject completely from all (safety) analysis sets
I1	ICF not obtained	
I2	ICF was signed after the other screening procedures; ICF wrong version was obtained.	
S1	If Patient did not take the drug ever	

Category Deviation code	Text description of deviation	Data exclusion
Subjects are excluded from PK analysis in case of these Protocol deviations:		Exclude subject from PK analysis set
I1	ICF not obtained	
I2	ICF was signed after the other screening procedures; ICF wrong version was obtained.	
S1	If Patient did not take the drug ever	
Subjects are excluded from PD analysis in case of these Protocol deviations:		Exclude subject from PD analysis set
S1	If Patient did not take the drug ever	
E1	Secondary Sjögren's syndrome	
I1	ICF not obtained	
I2	ICF was signed after the other screening procedures; ICF wrong version was obtained.	
I3	Diagnosis of primary Sjögren's syndrome	
I4	ESSDAI at screening/baseline ≥ 6	
I5	ESSPRI at screening/baseline ≥ 5	

If updates to this table are needed, an amendment to the SAP needs to be implemented prior to DBL.

5 Statistical methods for Pharmacokinetic (PK) parameters

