11.1 Analysis sets

For all analysis sets, subjects will be analyzed according to the study treatment(s) received.

The full analysis set will include all subjects that received any study drug.

The safety analysis set will include all subjects that received any study drug. The PK analysis set will include all subjects with at least one valid (i.e. not flagged for exclusion) PK concentration measurement, who received study drug and no protocol deviations with relevant impact on PK data.

The PD analysis set will include all subjects that received study drug and had no protocol deviations with relevant impact on PD data.

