7.1.2 Descriptive analyses

Subject demographics and other baseline characteristics

All data for background and demographic variables will be listed by treatment group and subject. Summary statistics will be provided by treatment group.

Relevant medical history, current medical conditions, results of laboratory screens, drug tests and any other relevant information will be listed by treatment group and subject.

Treatment

Data for study drug administration (rescue medication) and concomitant therapies will be listed by treatment group and subject.

Baseline concomitant medication related to pSS will be summarized by treatment group.

Summaries and listings of cumulative exposure to study drug (cumulative dose received over the treatment period) will be provided.

Heatmaps of exposure will be provided.

Vital signs

All vital signs data will be listed by treatment, subject, and visit/time and if ranges are available abnormalities (and relevant orthostatic changes) will be flagged. Summary statistics will be provided by treatment and visit/time.

ECG evaluations

All ECG data will be listed by treatment, subject and visit/time, abnormalities will be flagged. Summary statistics will be provided by treatment and visit/time.

In the protocol it was stated to use a longitudinal PK-QT model to check for concentration-dependent increase in QT. If this pooled analysis is done it will be presented in a separate report.

Clinical laboratory evaluations

All laboratory data will be listed by treatment, subject, and visit/time and if normal ranges are available abnormalities will be flagged. A separate listing is provided presenting all parameters in a subject with any abnormal values. Summary statistics will be provided by treatment and visit/time.

Adverse events

All information obtained on adverse events will be displayed by treatment and subject.

The number and percentage of subjects with adverse events will be tabulated by body system and preferred term with a breakdown by treatment. A subject with multiple adverse events within a body system is only counted once towards the total of this body system and treatment.

Heatmaps of neutropenia and rashes will be presented.

Liver and renal events will be listed and summarized using frequency tables.

Other safety evaluations

Immunogenicity

All immunogenicity results will be listed by subject and visit/time.

Infections

The frequency of infections will be tabulated.

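### The SAP takes dosed patients out of the safety set for consent-form deviations, although the protocol's safety set is everyone dosed

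*SAP*

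**What the plan says.** Protocol 11.1 sets one condition for the safety set, which is having been dosed: "The safety analysis set will include all subjects that received any study drug". It names no deviation that removes a dosed patient.

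SAP section 4 adds a second condition: "All subjects that received study drug and with no protocol deviations with relevant impact on safety will be included in the safety analysis set". Table 4-1 turns it into three codes, under the instruction "Exclude subject completely from all" safety analysis sets:

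- I1: no consent form.
- I2: "ICF was signed after the other screening procedures; ICF wrong version was obtained".
- S1: never dosed.

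SAP 1.1 says that the SAP "describes the implementation of the statistical analysis planned in the protocol". Where the SAP handles the QT modelling differently from the protocol, section 7.1.2 refers back to it: "In the protocol it was stated to use a longitudinal PK-QT model to check for concentration-dependent increase in QT". Section 4 has no such remark about the safety set.

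On a related matter, SAP 6.1.3.2 leaves out of the PD summaries and PD-set analyses any value measured more than 7 days after treatment stopped. Protocol 11.4 and SAP 6.1.1 both say that the ESSPRI model takes in every time point to week 13. Protocol 7.1 asks patients who stop treatment to keep attending.

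**The concern.** Safety and tolerability are a primary objective. The usual reason for a safety set of everyone dosed is that a harm in an exposed patient counts whatever else went wrong with that patient's conduct in the study. Under Table 4-1, an adverse event in a dosed patient who signed late or signed the wrong form version would drop out of the reported safety results. SAP 7.1.2 plans the main table as follows: "The number and percentage of subjects with adverse events will be tabulated by body system and preferred term with a breakdown by treatment". With 18 and 9 patients planned per arm, one missing patient shows in both numerator and denominator.

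The 7-day rule raises a smaller matter of the same kind. It discards ESSPRI values that the protocol takes trouble to collect, and an early stop can remove a patient from the primary efficacy analysis altogether.

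**Working it through.** **Safety set: the two rules compared**

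| Dosed patient with | Protocol 11.1 | SAP section 4 and Table 4-1 | Evident bearing on safety data? |
|---|---|---|---|
| No deviation | In | In | n/a |
| I1, no consent form | In | Out | None stated; there may be an ethical or legal bar on use |
| I2, late signature or wrong version | In | Out | None evident |

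S1 concerns patients who were never dosed, so it agrees with the protocol. The conflict is confined to I1 and I2. For I2 the SAP also conflicts with itself, because its general condition asks for a deviation that matters for safety and the table applies one that evidently does not. Protocol 9.1 counts an event as adverse only after written consent. In a late-signature patient the events that meet that definition therefore follow the signature, and I2 would still remove them.

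**Size per excluded patient**

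The plan gives no figure for this point. The inputs are the planned arm sizes in protocol 11.6. These reproduce: 24 evaluable patients / (1 - 0.10) = 26.7, rounded up to 27, split 2:1 into 18 and 9.

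- Share of an arm lost: 1/18 = 5.6% (CDZ173); 1/9 = 11.1% (placebo).
- Chance of seeing at least one case of an event with true rate p among n patients: 1 - (1 - p)^n.
- One-sided 95% upper bound on p when no case is seen: 1 - 0.05^(1/n).

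The event rates and the number of exclusions are assumptions.

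| CDZ173 patients kept | p = 5% | p = 10% | Upper bound, zero cases |
|---|---|---|---|
| 18 | 60.3% | 85.0% | 15.3% |
| 17 | 58.2% | 83.3% | 16.2% |
| 16 | 56.0% | 81.5% | 17.1% |

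The stated ESSPRI power of 86% does not depend on the safety-set rule.

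**7-day rule**

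Protocol Table 8-1 places the post-baseline ESSPRI assessments up to week 13 on Days 29, 57 and 85, with windows of 2, 3 and 3 days either side. A value is kept if visit day minus stop day is at most 7, so the earliest stop day that keeps it is visit day minus 7.

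| Visit | Earliest stop day that keeps the value | Range over the visit window |
|---|---|---|
| Day 29 | 22 | 20 to 24 |
| Day 57 | 50 | 47 to 53 |
| Day 85 | 78 | 75 to 81 |

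At nominal days, a stop before Day 78 loses the week-13 value. A stop before Day 22 loses every post-baseline value, and SAP 6.1.3.2 requires at least one for the primary analysis.

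An all-data run has a price, since off-treatment values may dilute the estimate. The approximate dilution is (stoppers / 18) x true difference x fraction of benefit lost. Assume 0 to 2 CDZ173 patients stop before Day 78 and keep attending, a true difference of 1 to 2 points, and none to all of the benefit lost. The dilution then runs from 0 to 2/18 x 2 x 1 = 0.22 points. The limit of two stoppers is an assumption; the 10% in protocol 11.6 is drop-out, which is a different quantity.

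**The case against.** The strongest reply is that consent is not a formality. Written consent before any assessment is the first inclusion criterion, and protocol 8.1 repeats it. A sponsor may be barred from using data gathered without valid consent, and I1 and I2 may exist for that reason. This stands in part. It is an argument about which data may be used, and it belongs to an ethics or legal decision. It does not turn a late signature into a deviation affecting safety, and the SAP does not offer it as the reason. The fix must therefore keep set membership and consent limits on data apart; otherwise an open-ended consent exception would undo the restoration.

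A second reply is that the case will be rare. Protocol section 4 bars enrolment for any failed entry criterion, and protocol 10.1 has monitors verify consent in full. A dosed I2 patient means that these checks failed or came too late. That stands, and it limits the size of the problem. It does not remove the conflict between the documents.

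Third, SAP 7.1.2 names no analysis set and says that all adverse event information will be displayed by patient. Loss from the tables is thus inferred from the instruction in Table 4-1. The inference is the natural one, since the table removes the patient from every safety set.

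On the 7-day rule, the reply largely succeeds. An on-treatment analysis is a legitimate choice in a non-confirmatory study. The SAP states it openly, and the excluded values still appear as dotted lines in the individual figures.

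**Conclusion.** The safety-set definitions conflict. Following the SAP as written could remove dosed patients from the results for a primary objective, and I2 does not meet the SAP's own condition. The public text neither flags nor justifies this; parts of the SAP are redacted, so nothing can be said about those. The size is conditional: 5.6% of the CDZ173 arm or 11.1% of the placebo arm per excluded patient, at planned arm sizes and with an unknown number of I2 cases, which may be zero. It should be fixed.

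Four stronger readings are tempting, and the documents do not support them.

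- A reader might infer that harms would escape oversight. SAE reporting (protocol 9.2.2) and the stopping rules (protocol 7.6) do not depend on an analysis set, so the loss is confined to the reported results.
- A reader might infer that the 7-day rule breaches the protocol. No protocol text expressly puts off-treatment ESSPRI values in the model; the wording about time points can mean scheduled visits, and continued attendance does not settle which values are modelled. The rule fits poorly with that wording, which justifies a sensitivity analysis and no more. That it governs the primary ESSPRI model is itself read from its place under SAP 6.1.
- A reader might count the SAP's lack of a full analysis set as a further fault. Protocol 11.1 defines that set in the same terms as the safety set, and SAP 6.1.3.2 already says who enters the primary analysis.
- A reader might object that codes I4 and I5 refer to screening/baseline while protocol 4.1 sets the cut-offs at screening. Protocol section 4 has eligibility checked at both visits, so this is editorial.

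**What to change.** 1. Amend SAP section 4 and Table 4-1 so that the safety set is everyone who took any study drug. Remove I2 as a safety-set exclusion and list it as a deviation. If an ethics or legal decision bars specific data (I1, or data collected before valid consent), withhold only those data, state the basis, and report by arm how many dosed patients are affected.

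2. As a secondary improvement, keep the 7-day rule and say in SAP 6.1.1 that it qualifies the statement about time points. Add one sensitivity run of the primary ESSPRI model on all observed values to week 13.

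The first change costs SAP wording; the SAP itself requires an amendment before database lock for any update to Table 4-1. The second costs one extra model run, and its estimate may be somewhat diluted by off-treatment values. No design, sample size or data collection changes.

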5.1 Variables

The following plasma pharmacokinetic parameters will be determined using the actual recorded sampling times on Day 1 and non-compartmental method(s) with Phoenix WinNonlin (Version 6.2 or higher): C_{max}, T_{max}, AUC_{0-7h} and AUC_{last}. Other PK parameters may be added as appropriate. After multiple doses, PK will be summarized in terms of trough concentration (C_{trough}).

PK parameters will be calculated as per Novartis Guidance on Standardization of Pharmacokinetic Parameters. The linear trapezoidal rule will be used for AUC calculation. Regression analysis of the terminal plasma elimination phase for the determination of T_{1/2} will include at least 3 data points after C_{max}. If the adjusted R² value of the regression analysis of the terminal phase will be less than 0.75, no values will be reported for T_{1/2}, AUC_{inf} and CL/F. The extrapolated part of the AUC_{inf} will not contribute to more than 20% of total AUC.

5.2 Descriptive analyses

The pharmacokinetics of CDZ173 will be evaluated in patients in the PK analysis set. CDZ173 plasma concentration data will be listed by treatment, subject, and visit/sampling time point. Descriptive summary statistics will be provided by treatment and visit/sampling time point, including the frequency (n, %) of concentrations below the LLOQ and reported as zero.

Summary statistics will include mean (arithmetic and geometric), SD, CV (arithmetic and geometric), median, minimum and maximum. An exception to this is Tmax where median, minimum and maximum will be presented. Concentrations below LLOQ will be treated as zero in summary statistics and for PK parameter calculations. A geometric mean will not be reported if the dataset includes zero values. Pharmacokinetic parameters will be listed by treatment and subject.

Corporate Confidential Information

5.2.1 Graphical presentation of results

Arithmetic mean (SD) and geometric mean (95% CI) plasma concentration data will be plotted over time.

Overlaying individual plasma concentration-time profiles will be generated along with concentration versus time profiles for individual subjects.

Relationships between exposure (average C_{trough} over time) and selected PD variables, **Corporate Confidential Information** will be explored by a graphical approach and descriptive statistics of exposure and PD variables will be provided.

6 Statistical methods for pharmacodynamic (PD) parameters

6.1 Primary objective

6.1.1 Variables

The primary aims of this study are to assess safety in patients with pSS and to investigate the effect of CDZ173 on efficacy (as measured by the ESSPRI) at study week 13. The statistical analysis model will include ESSPRI data from all time points up to study week 13. The

primary efficacy variable is the ESSPRI change from baseline (based on the mean of the below first 3 questions from the questionnaire):

- How severe has your dryness been during the last 2 weeks?
- How severe has your fatigue been during the last 2 weeks?
- How severe has your pain been during the last 2 weeks?

The other questions will be listed but not summarized. The safety and tolerability, as described in Section 7, will be summarized.

